8.25 Visit 25 (Week 46)

Subjects will have the following procedures performed/recorded prior to administration of study drug:

- Medical procedures
- Concomitant medication
- AEs
- IRT information
- Study drug administration (after all other visit assessments completed)

8.26 Visit 26 (Week 48)

Subjects will have the following procedures performed/recorded prior to administration of study drug:

- Weight
- Hematology, biochemistry, and urine (dipstick) for clinical laboratory values
- Urine pregnancy test for women of childbearing potential
- PASI (will not be performed in subjects with generalized pustular PSO)
- PGA (will not be performed in subjects with generalized pustular PSO)
- Itch Numeric Rating Scale
- DLQI
- mNAPSI (for subjects with psoriatic nail disease)
- Subject PsA assessments (HAQ-DI, Patient's Assessment of Arthritis Pain, and PGADA for subjects with PsA)
- Physician PsA assessments (swollen and tender joint counts and PhGADA for subjects with PsA)
- Pustular and erythrodermic PSO assessments (Global Improvement Score, JDA Severity Index, and CGI-I for subjects with generalized pustular PSO or CGI-I for subjects with erythrodermic PSO)
- Medical procedures
- Concomitant medication
- AEs
- IRT information
- Study drug administration (after all other visit assessments completed)

8.27 Visit 27 (Week 50)

Subjects will have the following procedures performed/recorded prior to administration of study drug:

- Medical procedures
- Concomitant medication
- AEs
- IRT information
- Study drug administration (after all other visit assessments completed)

8.28 Visit 28 (Week 52)

Subjects will have the following procedures performed/recorded:

- Blood pressure
- 12-lead ECG
- Weight
- Hematology, biochemistry, and urine (dipstick) for clinical laboratory values, including beta-D-glucan and sialylated carbohydrate antigen KL-6
- Urine pregnancy test for women of childbearing potential
- Chest x-ray
- IGRA
- Subject TB questionnaire
- Plasma for PK and immunogenicity samples
- Physical examination, including evaluation for signs and symptoms of TB
- PASI (will not be performed in subjects with generalized pustular PSO)
- PGA (will not be performed in subjects with generalized pustular PSO)
- Itch Numeric Rating Scale
- BSA affected by PSO (will not be performed in subjects with generalized pustular PSO)
- DLQI
- mNAPSI (for subjects with psoriatic nail disease)
- Subject PsA assessments (HAQ-DI, Patient's Assessment of Arthritis Pain, and PGADA for subjects with PsA)
- Physician PsA assessments (swollen and tender joint counts and PhGADA for subjects with PsA)
- Pustular and erythrodermic PSO assessments (Global Improvement Score, JDA Severity Index, and CGI-I for subjects with generalized pustular PSO or CGI-I for subjects with erythrodermic PSO)
- Medical procedures
- Concomitant medication
- AEs
- IRT information

8.29 Safety Follow-Up Visit

Subjects will have the following procedures performed/recorded 10 weeks after the last dose of study drug:

- Blood pressure
- Physical examination

- Hematology, biochemistry, and urine (dipstick) for clinical laboratory values
- Urine pregnancy test for women of childbearing potential
- Plasma for PK and immunogenicity samples
- AEs
- Medical procedures
- Concomitant medications

8.30 Withdrawal Visit

Subjects will have the following procedures performed/recorded:

- Blood pressure
- 12-lead ECG
- Weight
- Hematology, biochemistry, and urine for clinical laboratory values, including beta-D-glucan and sialylated carbohydrate antigen KL-6
- Urine pregnancy test for women of childbearing potential
- Plasma for PK and immunogenicity samples
- Physical examination, including evaluation for signs and symptoms of TB
- Chest x-ray
- IGRA
- Subject TB questionnaire
- PASI (will not be performed in subjects with generalized pustular PSO)
- PGA (will not be performed in subjects with generalized pustular PSO)
- Itch Numeric Rating Scale
- DLQI
- BSA affected by PSO (will not be performed in subjects with generalized pustular PSO)
- mNAPSI (for subjects with psoriatic nail disease)
- Subject PsA assessments (HAQ-DI, Patient's Assessment of Arthritis Pain, and Patient's Global Assessment of Disease Activity for subjects with PsA)
- Physician PsA assessments (swollen and tender joint counts and Physician's Global Assessment of Disease Activity for subjects with PsA)
- Pustular and erythrodermic PSO assessments (Global Improvement Score, JDA Severity Index, and CGI-I for subjects with generalized pustular PSO or CGI-I for subjects with erythrodermic PSO)
- Medical procedures

- Concomitant medication
- AEs
- IRT information

8.31 Unscheduled Visit

Unscheduled visits will be permitted during the study to allow follow-up of abnormal laboratory results or physical findings. Assessments during unscheduled visits may include:

- Blood pressure
- Physical examination
- Hematology, biochemistry, and urine for clinical laboratory values
- Urine pregnancy test for women of childbearing potential
- AEs
- Medical procedures
- Concomitant medications

9 ASSESSMENT OF EFFICACY

All assessments will be completed as outlined in the Schedule of Study Assessments (Table 5–1).

9.1 Psoriasis Area Severity Index (PASI)

The PASI is the most commonly used and validated assessment for grading the severity of PSO in clinical studies (Feldman, 2004). The PASI quantifies the severity and extent of the disease and weighs these with the percentage of BSA involvement.

The percent area of involvement (BSA%) is estimated across 4 body areas; head, upper limbs, trunk, and lower limbs and then transferred into a grade (Table 9–1).

The Investigator assesses the average redness, thickness, and scaliness of lesions in each body area (each on a 5-point scale); 0=none, 1=slight, 2=moderate, 3=marked, and 4=very marked.

The PASI score ranges from 0 to 72 with a higher score indicating increased disease severity.

Table 9–1: Body areas for calculation of percent BSA for PASI

Body area	Details of area	BSA	Degree of involvement of body area ^a
Head	Face, back of head	10%	0 to 6
Upper limbs	Left, right, upper lower, flexor surface, extensor surface	20%	0 to 6
Trunk	Front, back, groin	30%	0 to 6
Lower limbs	Left, right, upper lower, flexor surface, extensor surface, including buttocks	40%	0 to 6
Total		100%	

BSA=body surface area; PASI=Psoriasis Area and Severity Index

^a Where 0=none; 1=1% to <10% affected, 2=10% to <30% affected, 3=30% to <50% affected, 4=50% to <70% affected, 5=70% to <90% affected, 6=90% to 100% affected

The PASI50, PASI75, PASI90, and PASI100 responses are based on at least 50%, 75%, 90%, and 100% improvement in the PASI score.

9.2 BSA affected by psoriasis

The BSA palm method will be used for the evaluation of BSA as follows:

Body surface area estimation uses the palm (subject's flat hand and thumb together, fingers included) as representing around 1% of the total BSA.

- Subject's palm=1%
- Head and neck=10% (10 palms)
- Upper extremities=20 % (20 palms)
- Trunk=30% (30 palms)
- Lower extremities=40 % (40 palms)
- Total BSA=100%

9.3 Physician's Global Assessment of Psoriasis (PGA)

A static PGA for PSO will be used to assess disease severity in all subjects during the study. The Investigator will assess the overall severity of PSO using the following 5-point scale:

Physician's Global Assessment		
Score	Short Descriptor	Definition
0	Clear	No signs of psoriasis; post-inflammatory hyperpigmentation may be present
1	Almost clear	No thickening; normal to pink coloration; no to minimal focal scaling

2	Mild	Just detectable to mild thickening; pink to light red coloration; predominately fine scaling
3	Moderate	Clearly distinguishable to moderate thickening; dull to bright red, clearly distinguishable to moderate thickening; moderate scaling
4	Severe	Severe thickening with hard edges; bright to deep dark red coloration; severe/coarse scaling covering almost all or all lesions

The PGA score will be entered into the eCRF.

9.4 Dermatology Life Quality Index (DLQI)

The Dermatology Life Quality Index (DLQI) is a questionnaire designed for use in adult subjects with PSO. The DLQI is a skin disease-specific questionnaire aimed at the evaluation of how symptoms and treatment affect patients' HRQoL. This instrument asks subjects about symptoms and feelings, daily activities, leisure, work and school, personal relationships and treatment. It has been shown to be valid and reproducible in PSO patients. The DLQI score ranges from 0 to 30 with higher scores indicating lower HRQoL. A ≥ 4 -point change in the DLQI score (DLQI response) has been reported to be meaningful for the patient (within-patient minimal important difference); a DLQI absolute score of ≤ 1 indicates DLQI remission (ie, no or small impact of the disease on HRQoL) (Basra et al, 2015). Subjects will be asked to complete the DLQI as outlined in the Schedule of Study Assessments (Table 5-1).

Study site personnel should ensure that each subject completes the instrument prior to leaving the study site.

Responses to the DLQI will be obtained, and study staff should respond in the eCRF whether or not it was completed.

9.5 Modified Nail Psoriasis Severity Index (mNAPSI)

Subjects with psoriatic nail disease will have a target nail selected at the Baseline visit for evaluation using the mNAPSI. The nail selected should be the most affected nail observed at Baseline and should be the only one assessed throughout the study. The target nail will be scored (0 to 3) for onycholysis/oil drop dyschromia, nail plate crumbling, and pitting and will be scored (0 for "no" or 1 for "yes") for leukonychia, nail bed hyperkeratosis, splinter haemorrhages and red spots in the lunula.

Data will be entered into the eCRF.

9.6 Itch Numeric Rating Scale

The Itch Numeric Rating Scale has been developed as a simple, single item instrument to assess the patient-reported severity of itch at its most intense during the past 24h period. Subjects indicate itch severity by circling the integer that best describes the worst level of itching due to PSO in the past 24h period on an 11-point scale anchored at 0, representing "no itching" and 10, representing "worst itch imaginable" (Kimball et al, 2016).

9.7 Assessments for subjects with PsA

9.7.1 ACR20, ACR50, and ACR70 responses

For subjects with PsA, the ACR20, ACR50, and ACR70 response will be evaluated. The assessments are based on a 20%, 50%, 70% or greater improvement in the number of tender joints and swollen joints each and a 20%, 50%, 70% or greater improvement in at least 3 of the 5 remaining core set measures: Patient's and Physician's Global Assessments of Disease Activity (Section 9.7.8 and Section 9.7.7, respectively), Patient's Assessment of Arthritis Pain (Section 9.7.6), HAQ-DI (Section 9.7.5), and C-reactive protein (CRP).

9.7.2 Swollen and tender joint counts (66/68 joints evaluation)

The following 68 joints are to be examined for tenderness by the Principal Investigator, another delegated physician, or an appropriately qualified medical professional (based on local requirements) who has had documented training on how to perform these assessments correctly. Preferably the same assessor should evaluate the subject at each arthritis assessment.

- Upper body (6): bilateral temporomandibular, sternoclavicular, and acromioclavicular joints
- Upper extremity (34): bilateral shoulders, elbows, wrists (includes radiocarpal, and carpal and carpometacarpal bones considered as a single unit), MCP I, II, III, IV, and V, thumb interphalangeals (IP), PIP II, III, IV, and V and distal interphalangeals (DIP, II, III, IV, and V)
- Lower extremity (28): bilateral hips, knees, ankles, tarsi (includes subtalar, transverse tarsal, and tarsometatarsal considered as a single unit), metatarsophalangeals (MTP I, II, III, IV, and V), great toe interphalangeals, and proximal interphalangeals (PIP II, III, IV, and V)

The assessment for swelling is made on 66 joints from the above list. The hip joints are excluded. Artificial and ankylosed joints are excluded from both tenderness and swelling assessments.

These assessments are completed as outlined in the Schedule of Study Assessments (Table 5–1).

Table 9–2: Swelling and tenderness grading

Grade	Swelling response (66)	Tenderness response (68)
0	None	None (not tender)
1	Detectable	Positive (tenderness)

9.7.3 Swollen and tender joint counts (28 joints evaluation)

The following 28 joints will be used for calculation of the DAS28(CRP).

- Upper extremity (26): bilateral shoulders, elbows, wrists (includes radiocarpal, and carpal and carpometacarpal bones considered as a single unit), MCP I, II, III, IV, and V, thumb interphalangeals (IP), PIP II, III, IV, and V
- Lower extremity (2): knees

9.7.4 Disease Activity Score

The DAS28(CRP) will be calculated using CRP (mg/dL) (see Table 12–1) and the Patient's Global Assessment of Disease Activity (VAS) (see Section 9.7.8).

The joint assessment utilized for the DAS calculation will be based on 28 of the joints assessed for the 66/68-joint assessments (see Section 9.7.2, using the same 2-point scale for the assessment of swelling and tenderness of each joint.

DAS28(CRP) is calculated as follows:

$$DAS28(CRP) = 0.56 \cdot \sqrt{TJC} + 0.28 \cdot \sqrt{SJC} + 0.014 \cdot PGADA + 0.36 \cdot \ln(CRP + 1) + 0.96$$

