3.9 Changes to protocol-defined analyses

The definitions of the Analysis Sets have been clarified.

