A subject will be classified as receiving prior systemic therapy for psoriasis if they ever received previous biologic therapy, previous systemic therapy (non-biologic), or previous systemic chemophototherapy or phototherapy. Subjects who never received previous biologic therapy, previous systemic therapy (non-biologic), or previous systemic chemophototherapy or phototherapy will be classified as not receiving prior systemic treatment for psoriasis.

- Prior systemic treatment for PsA (only PsAS): yes, no

A subject will be classified as receiving prior systemic treatment for PsA if they ever received prior medications with PsA indication. Exclude any medications that are applications. Everything remaining after this step should be considered a systemic treatment for PsA.

- Prior anti-TNF therapy used: yes, no
- Prior exposure to at least 2 systemic treatments out of phototherapy, methotrexate, and cyclosporine (with no previous biologic exposure): yes, no
- Itch Numeric Rating Scale at Baseline
- PhGADA (only PsAS)
- PGADA (only PsAS)
- PGAAP (only PsAS)
- Tender joint count (only PsAS)
- Swollen joint count (only PsAS)
- HAQ-DI (only PsAS)
- CRP (mg/L) (only PsAS)
- DAS28 (CRP) (only PsAS)
- DAS28 (CRP) (only PsAS): <2.6 (remission), >=2.6 to <= 3.2 (low disease activity), >3.2 to <=5.1 (middle disease activity), and >5.1 (high disease activity)
- JDA score (only GPPS)

Furthermore, psoriasis Baseline characteristics will be tabulated:

- Presence of concomitant PsA at Baseline: yes, no

The presence of concomitant PsA at Baseline will be based on data queried directly in eCRF.

- Presence of Nail psoriasis: yes, no

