8.3 Analysis of other efficacy variables

A combination of both inferential and descriptive statistics will be used to analyze data collected up to Week 16 for the other efficacy variables. No adjustment for multiplicity will be made. After Week 16, data will generally be summarized using descriptive statistics only, unless otherwise specified. The general rules for which treatment groups will be used to

summarize data and how missing data will be handled across study periods are outlined in [Section 3.6](#) and [Section 4.2](#). Any exceptions are noted in the relevant section below.

[Table 8–3](#) presents an overview of the analysis of other efficacy variables.

Table 8–3: Overview of analysis of other efficacy variables

Population	Other efficacy variable	Analysis Set
Double-Blind Overall, Escape Arm, Cohort erythrodermic PSO	PASI50, PASI75, PASI90, and PASI100	FAS, EPS
	PGA clear or almost clear (with at least 2-category improvement)	
	Absolute and percent change from Baseline in PASI score	
	PGA score distribution	
	Absolute and percent change from Baseline in the BSA affected by PSO	
Double-Blind Overall	Time to onset of action, defined as the time to PASI50	FAS
	Time to onset of action, defined as the time to PASI75	
	Time to onset of action, defined as the time to PASI90	
	Time to onset of action, defined as the time to PASI100	
Double-Blind Overall, Escape Arm, Cohort Overall	Change from Baseline in DLQI mean scores, percent of subjects achieving MCID, and percent achieving DLQI remission	FAS, CFAS
Double-Blind Overall, Escape Arm, Cohort Overall	Change from Baseline in Itch Numeric Rating Scale mean scores and percent of subjects achieving MCID	FAS, CFAS
Double-Blind PsA, Escape Arm	ACR20, 50, 70 and change from Baseline in all individual ACR core components in the subpopulation of subjects with PsA at Baseline	PsAS
	Change from Baseline in DAS28(CRP) and CRP (mg/L)	
Double-Blind NAPSI, Escape Arm	Change from Baseline in mNAPSI in the subpopulation of subjects with nail disease at Baseline	NAPSI
Cohort overall	Clinical Global Impressions of Improvement (CGI-I)	CFAS
Cohort generalized pustular PSO	Global Improvement Score	GPPS
	Japanese Dermatological Association (JDA) severity index	

Table 8–4: Overview of analysis of variables in interim analysis

Population	Variable	Period	Analysis Set
Disposition and important protocol deviations as planned for final CSR			
Demographic and baseline characteristics as planned for final CSR			

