Primary and secondary efficacy variables as planned for final CSR			
Other efficacy variables			
Double-Blind Overall, Cohort erythrodermic PSO	PASI50, PASI75, PASI90, and PASI100	Initial and Maintenance*	FAS, EPS
	PGA clear or almost clear (with at least 2-category improvement)		
	Absolute and percent change from Baseline in PASI score		
	PGA score distribution		
	Absolute and percent change from Baseline in the BSA affected by PSO		
Double-Blind Overall	Time to onset of action, defined as the time to PASI50	Initial	FAS
Double-Blind Overall, Cohort Overall	Change from Baseline in DLQI mean scores, percent of subjects achieving MCID, and percent achieving DLQI remission	Initial and Maintenance*	FAS, CFAS
	Change from Baseline in Itch Numeric Rating Scale mean scores and percent of subjects achieving MCID		
Double-Blind PsA	ACR20, 50, 70 and change from Baseline in all individual ACR core components in the subpopulation of subjects with PsA at Baseline	Initial and Maintenance*	PsAS
	Change from Baseline in DAS28(CRP) and CRP (mg/DL)		
Double-Blind NAPSI	Change from Baseline in mNAPSI in the subpopulation of subjects with nail disease at Baseline	Initial and Maintenance*	NAPSIS
Cohort overall	Clinical Global Impressions of Improvement (CGI-I)	Initial and Maintenance*	CFAS

Table 8–4: Overview of analysis of variables in interim analysis

Population	Variable	Period	Analysis Set
Cohort generalized pustular PSO	Global Improvement Score	Initial and Maintenance*	GPPS
	Japanese Dermatological Association (JDA) severity index score		
PK/PD variables as planned for final CSR			
Safety variables as planned for final CSR			

*: Maintenance Period carried out at Week 24 instead of Week 52 as in the final analysis.

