8.3.15 Disease Activity Score DAS28(CRP) (28 joints evaluation)

The DAS28(CRP) will be calculated using CRP (mg/L) (see Table 10-1) and the Patient's Global Assessment of Disease Activity (VAS) (see Section 8.3.12). The joint assessment utilized for the DAS calculation will be based on 28 of the joints assessed for the 66/68-joint assessments (see Protocol Section 9.7.3)

- Upper extremity (26): bilateral shoulders, elbows, wrists (includes radiocarpal, and carpal and carpometacarpal bones considered as a single unit), MCP I, II, III, IV, and V, thumb interphalangeals (IP), PIP II, III, IV, and V
- Lower extremity (2): knees

using the same 2-point scale for the assessment of swelling and tenderness of each joint.

DAS28(CRP) is calculated as follows:

$$DAS28(CRP) = 0.56x\sqrt{TJC} + 0.28x\sqrt{SJC} + 0.014xPGADA + 0.36x\ln(CRP + 1) + 0.96$$

where TJC=tender joint count and SJC=swollen joint count.

The DAS28(CRP) will be evaluated for subjects with psoriatic arthritis (PsA). The analysis will be based on the PsA Set including only subjects with 3 or more tender joints and 3 or more swollen joints at Baseline on Observed case and LOCF imputed data.

- If there are missing observations for tender or swollen joints, then the remaining observations will be assessed and weighted by dividing by number of non-missing and by multiplying by 28.
- If a joint is not evaluable at Baseline, then that joint is set to missing throughout the study.
- If at least 1 item of DAS28(CRP) is available for a visit, LOCF will be applied to impute values of those individual components which are missing.
- For CRP values below the lower limit of quantification, half the lower limit will be used as the imputed value. The lower limit of quantification may vary depending on the assay used and the imputed value will vary with it. For example, if the value is

presented as <3.0 , then 1.5 will be used and if <0.1 is presented, then 0.05 will be used.

The DAS28(CRP) Disease Activity Classification will be presented in the categories Remission: <2.6 , LDA: ≥ 2.6 to ≤ 3.2 , MDA: >3.2 to ≤ 5.1 , HDA: >5.1 and Missing by visit and by randomized treatment group during Initial Period and by blinded maintenance or escape maintenance treatment group during Maintenance Period in Observed case data.

A line plot will be generated to present change from Baseline in DAS28(CRP) score by randomized treatment group through Week 24/52.

8.3.16 mNAPSI (change from Baseline)

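### Protocol 9.7.4 and SAP 8.3.15 put CRP into the same DAS28(CRP) formula in units that differ tenfold, and the difference is not declared

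*Protocol*

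**What the plan says.** Protocol 9.7.4: "The DAS28(CRP) will be calculated using CRP (mg/dL". SAP 8.3.15: "The DAS28(CRP) will be calculated using CRP (mg/L".

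Both sections then give the same expression: 0.56√TJC + 0.28√SJC + 0.014·PGADA + 0.36·ln(CRP + 1) + 0.96. Neither converts CRP. The laboratory tables they point to (Protocol Table 12-1, SAP Table 10-1) list C-reactive protein without a unit.

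Elsewhere the SAP mostly uses mg/L: in the Baseline list of 6.2 and in Table 8-3, "Change from Baseline in DAS28(CRP) and CRP (mg/L". The matching row of Table 8-4, for the interim analysis, reads "Change from Baseline in DAS28(CRP) and CRP (mg/DL". The JDA severity index takes CRP in mg/dL in both documents (Protocol Table 9-4, SAP Table 8-7).

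Only the SAP sets activity categories: "<2.6 (remission), >=2.6 to <= 3.2 (low disease activity), >3.2 to <=5.1 (middle disease activity), and >5.1 (high disease activity" (6.2, repeated in 8.3.15). For CRP below the limit of quantification, SAP 8.3.15 substitutes half the limit. Its two examples, limits of 3.0 and 0.1, carry no unit.

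SAP 3.9, on changes from the protocol, contains one sentence: "The definitions of the Analysis Sets have been clarified".

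**The concern.** A tenfold change of unit would be harmless if CRP entered the score linearly with a coefficient adjusted to match, or as a pure logarithm, where it would only add a constant. Here it enters as ln(CRP + 1) with an unchanged coefficient. The shift therefore depends on each subject's CRP and does not cancel when a Baseline score is subtracted from a later one.

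The variable is reported in several ways: at Baseline (SAP 6.2), as ANCOVA differences from placebo with confidence intervals and p-values during the Initial Period (SAP 8.3.9), and by activity category at each visit (SAP 8.3.15). A programmer working from the protocol and one working from the SAP would produce different values for all of these. SAP 9.3 shows that interim results already exist, so the interim and final scores need to be known to share a unit.

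**Working it through.** There is no stated figure to reproduce, since nothing in either document is calculated from the CRP unit. The check evaluates the documents' own formula in both units.

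**Inputs from the documents:** the coefficient 0.36 and the form ln(CRP + 1) (Protocol 9.7.4, SAP 8.3.15); the cut-offs 2.6, 3.2 and 5.1 (SAP 6.2 and 8.3.15).

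**Assumed inputs:** all CRP values, joint counts and PGADA values below. Neither document gives a CRP distribution for these subjects.

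**Shift in the score.** For CRP in mg/L, the SAP score minus the protocol score is 0.36 × [ln(CRP + 1) − ln(CRP/10 + 1)].

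| CRP (mg/L) | Shift |
|---|---|
| 1 | 0.36 × (ln 2 − ln 1.1) = 0.22 |
| 3 | 0.36 × (ln 4 − ln 1.3) = 0.40 |
| 10 | 0.36 × (ln 11 − ln 2) = 0.61 |
| 20 | 0.36 × (ln 21 − ln 3) = 0.70 |
| 50 | 0.36 × (ln 51 − ln 6) = 0.77 |
| 100 | 0.36 × (ln 101 − ln 11) = 0.80 |

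The shift rises with CRP towards 0.36 × ln 10 = 0.83. The low-activity band is 3.2 − 2.6 = 0.6 wide, so at 10 mg/L the shift already exceeds the whole band.

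**Category moves**, classified with the SAP cut-offs:

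- TJC 1, SJC 1, PGADA 20, CRP 10 mg/L. The terms other than CRP sum to 0.56 + 0.28 + 0.28 + 0.96 = 2.08. With mg/dL the score is 2.08 + 0.36 ln 2 = 2.33 (remission); with mg/L it is 2.08 + 0.36 ln 11 = 2.94 (low).
- TJC 3, SJC 3, PGADA 30, CRP 10 mg/L: 3.08 (low) against 3.70 (middle).
- TJC 10, SJC 8, PGADA 70, CRP 20 mg/L: 4.90 (middle) against 5.60 (high).

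**Change from Baseline.** For a CRP fall from 20 to 3 mg/L, the CRP term contributes:

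- in mg/dL: 0.36 × (ln 1.3 − ln 3) = −0.30
- in mg/L: 0.36 × (ln 4 − ln 21) = −0.60

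The shift falls from 0.70 at Baseline to 0.40 at the later visit, so 0.30 of it stays in the change score.

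**The case against.** The best counter-argument is that the SAP is the operative document for analysis. Protocol section 14 defers statistical detail to it, its calculation section states mg/L, and 6.2 and Table 8-3 agree. The cut-offs appear only in the SAP, so no sentence applies them to a score explicitly computed in mg/dL. A reader might infer that the remission and low-activity rates will be wrong. The documents do not support that: they show two rules that give different scores and rates, and a risk of misprogramming.

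A reader might also take Table 8-4 as evidence that the interim DAS28 used mg/dL. It is not. In that row the unit follows CRP, which is reported as a variable in its own right; it does not describe the input to the score. Set against the parallel row of Table 8-3, it is a labelling inconsistency.

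Nor do the documents prove that mg/L is the correct unit. Neither formula cites a source or says which unit its coefficients were derived for. The SAP's prevailing usage is a reason to expect mg/L, but it does not settle the question.

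Finally, the reach is small. DAS28(CRP) is an other efficacy variable, unadjusted for multiplicity and outside the testing sequence. SAP 8.3.15 analyses it in the PsA Set "including only subjects with 3 or more tender joints" and 3 or more swollen joints. ACR response uses percentage change in CRP, which does not depend on the unit.

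These points limit the consequence. They do not remove the contradiction: the two calculation sections still state incompatible inputs, and nothing in the SAP says that one replaces the other.

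**Conclusion.** The point holds as an undeclared inconsistency between protocol and SAP in the definition of a reported variable. At most one unit can fit the coefficients and the 2.6/3.2/5.1 cut-offs, and the documents do not establish which.

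The size rests on assumed CRP values. Over 1 to 50 mg/L the difference is about 0.2 to 0.8 units, and the limit of 0.83 is approached only at very high CRP. Differences of this size are enough to change activity categories in the illustrative subjects and to double the CRP contribution to change in the example shown. How many subjects would move cannot be said without their CRP, joint counts and PGADA.

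The effect is confined to DAS28(CRP) in subjects with psoriatic arthritis. PASI75, PGA response, PASI90, DLQI and itch at Week 16 are untouched.

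**What to change.** 1. Reconcile Protocol 9.7.4 and SAP 8.3.15 to one CRP unit, confirmed against the source of the formula and the cut-offs, and cite that source. The SAP's own usage in 6.2, Table 8-3 and 8.3.15 is mg/L.
2. State the unit in which the laboratory reports CRP and the conversion applied before the score is computed. This matters the more because the JDA index needs the same analyte in mg/dL.
3. Give the unit of the quantification limit used for half-limit substitution in SAP 8.3.15.
4. Correct the CRP label in SAP Table 8-4 so that it matches Table 8-3.
5. If the agreed unit differs from the protocol's, list it in SAP 3.9.
6. Confirm which unit the interim DAS28(CRP) values used. If it was not the agreed one, recompute them so that interim and final results are comparable.

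The cost is wording and one programming check, plus a rerun of the interim DAS28 outputs if the check shows a mismatch.
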